10.3 Investigational Product Handling

The Investigator and Research Pharmacist (if relevant) will be provided with *Investigational Product Handling Guidelines* that will provide details regarding the packaging and labeling requirements, receipt of investigational product, dispensing and accountability procedures, preparation instructions, storage and stability of the Investigational product and disposition of the Investigational Product.

10.4 Investigational Product Accountability

The Investigator and Study Pharmacist (if relevant) are responsible for ensuring that all study supplies received at the site are inventoried and accounted for throughout the study. The dispensing of study substrate to the subject must be documented in the respective accountability form. The study Investigational Product must be stored in a limited access area or in a locked cabinet under appropriate environmental conditions. Unused study materials must be available for verification by the sponsor's site monitor during on-site monitoring. The destruction of unused study materials (both, expired or unexpired) will be documented on the return/disposition form. The Sponsor will authorize destruction of excess supplies on site according to local policy. In this case, before proceeding, the site must seek authorization from the Sponsor using the return/destruction form and this must also be documented on the Study Supply Return Form.

Study substrate should be dispensed under the supervision of the investigator, a qualified member of the investigational staff, or by hospital clinical pharmacist.

11 ETHICS & REGULATORY CONSIDERATIONS

The study will be conducted by Conatus as a Phase 2 study of emricasan in both the USA and in Europe. As such, regulatory requirements that are relevant for pharmaceutical investigations in all countries will be applicable during the study are to be conducted and overseen by Conatus.

Conatus will obtain for the main study IND-6556-17 the applicable regulatory approvals for the use of clinical data from both regulatory authorities (if relevant) and ethics committees (IRBs).

Exalenz Bioscience Ltd.	Last update: May 24, 2017
Study Title: Companion protocol for the ¹³ C-Methacetin Breath Test using the BreathID® MCS System for Conatus phase 2 study of Emricasan, an Oral Caspase Inhibitor, under protocol IDN-6556-17 (IND111463)	Protocol: CON-EX-0217 Version: 2.0
Document Nº: CSP000001	Page 27 of 28

12 SAFETY CONSIDERATIONS

All adverse events (AE), serious adverse events (SAE), suspected unexpected serious adverse reactions (SUSAR) and unanticipated adverse device effects (UADE) possibly or probably related to the use of the MBT product or related to the MBT procedure will be collected and reported according to local regulations.

Safety assessments of the Conatus study drug will be performed as described in Conatus protocol IDN-6556-17: *Safety Assessments*.

13 SUBJECT CONFIDENTIALITY

The subject's name and personal data will remain confidential and will not be published in any way. All data will be coded and stored in locked offices or on password protected computers.

14 MONITORING AND QUALITY ASSURANCE

This study is a companion protocol that will use the data generated by the Conatus Phase 2 study of emricasan under protocol IDN-6556-17. Conatus will ensure compliance with GCP, local regulations and scientific integrity and will manage and oversee the study conduct.

15 PUBLICATION POLICY AND FINANCE

It is intended that the results of the companion study will be reported and disseminated at international conferences and in peer-reviewed scientific journals. The policy regarding publications appears in the non-disclosure agreement signed by each study participant prior to signing of the contract.

16 FINANCIAL ASPECTS

The BreathID® MCS device and test kit including a nasal cannula and a solution containing ¹³C-Methacetin will be provided by Exalenz Bioscience. Conatus will be responsible for the funding of regulatory approvals in regards to the main protocol and administration as well as for the funding for study support of staff at local sites.

17 STUDY TERMINATION

This study is a companion protocol that will use the data generated by Conatus from their Phase 2 study of emricasan under protocol IDN-6556-17. Conatus will be responsible for study termination procedures, when applicable.

Exalenz Bioscience Ltd.	Last update: May 24, 2017
Study Title: Companion protocol for the ¹³C-Methacetin Breath Test using the BreathID® MCS System for Conatus phase 2 study of Emricasan, an Oral Caspase Inhibitor, under protocol IDN-6556-17 (IND111463)	Protocol: CON-EX-0217 Version: 2.0
Document Nº: CSP000001	Page 28 of 28

1 ABBREVIATIONS

AE	- Adverse Event
CDOB	- Cumulative Delta over Baseline
CI	- Confidence Interval
CL	- Confidence Limits
CO ₂	- Carbon dioxide
cPDRxx	- Cumulative Percentage Dose Recovery at xx minutes from ingestion
CRF	- Case Report Form
CSR	- Clinical Study Report
CTP	- Child-Turcotte-Pugh (score)
DOB	- Delta over Baseline
eCRF	- Electronic Case Report Form
EGD	- Esophagogastroduodenoscopy
GCP	- Good Clinical Practice
HCC	- Hepatocellular Carcinoma
HE	- Hepatic Encephalopathy
HR	- Hazard Ratio
IDE	- Investigational Device Exemption
ITT	- Intent to treat (population)
MBT	- ¹³ C-Methacetin Breath Test
MCS	- Molecular Correlation Spectrometry
MELD	- Model for Endstage Liver Disease
NAFLD	- Nonalcoholic Fatty Liver Disease
NASH	- Nonalcoholic Steatohepatitis
OPTN	- Organ Procurement and Transplantation Network
PDR	- Percent Dose Recovered (expressed as % per hour)
PP	- Per Protocol (population)
SAE	- Serious Adverse Event
SAP	- Statistical Analysis Plan
SBP	- Spontaneous Bacterial Peritonitis
SD	- Standard Deviation
SF	- Screen Failures
SUSAR	- Suspected unexpected serious adverse reaction
TIPS	- Transjugular Intrahepatic Shunt
UADE	- Unanticipated Adverse Device Effect
US	- United States (of America)
USA	- United States of America

Exalenz Bioscience Ltd.	Last update: August 8, 2019
SAP for Protocol CON-EX-0217: Companion protocol for the ¹³C-Methacetin Breath Test using the BreathID® MCS System for Conatus phase 2 study of Emricasan, an Oral Caspase Inhibitor, under protocol IDN-6556-17 (IND111463)	Document Version: 1.0
Document N°: CSD00109	Page 5 of 21

2 INTRODUCTION

This Statistical Analysis Plan (SAP) (for Exalenz' companion study protocol: CON-EX-0217) was developed based on the original study protocol version 2.0, dated 24 May 2017 and is a more detailed companion to the “Statistical Methods” section of the study protocol.

The companion protocol and this SAP describe how Exalenz intends to use the clinical data being obtained during the study conducted by Conatus Pharmaceuticals Inc. (Conatus) for study IDN-6556-17 (Emricasan) being conducted under IND 111463.

When differences exist in methods, descriptions or explanations provided in the protocol and this SAP, the SAP prevails.

Since this study is a companion to a pharmaceutical company's study, the data management for the main study can independently determine as to when a data freeze or a data lock shall be performed. Therefore, for the Exalenz companion protocol purposes, any amendments to the SAP will be made prior to Exalenz independently accessing the data from the database freeze or lock. In case additional analyses not described in the final SAP or deviations from the final SAP are required, they will be documented in the clinical study report (CSR).

3 STUDY OBJECTIVES AND ENDPOINTS

3.1 *Study Objectives*

The data generated in this companion study will be used to validate an algorithm developed under parallel Exalenz studies. Additionally, the companion study aims to evaluate the capabilities of the MBT to assess the severity of Nonalcoholic Steatohepatitis (NASH), predict clinical outcome (hepatic decompensation) events and monitor changes of MBT results in subjects with and without NASH treatment.

Exalenz Bioscience Ltd.	Last update: August 8, 2019
SAP for Protocol CON-EX-0217: Companion protocol for the ^{13}C-Methacetin Breath Test using the BreathID® MCS System for Conatus phase 2 study of Emricasan, an Oral Caspase Inhibitor, under protocol IDN-6556-17 (IND111463)	Document Version: 1.0
Document N°: CSD00109	Page 6 of 21

3.1.1 Primary Objective

- To validate the ability of the MBT to predict any hepatic decompensation event (considering all hepatic decompensation events as defined in section 8.4.1) using a predefined cut-off of $\text{PDR}_{\text{peak}} \leq 5.5\%/\text{h}$ (see **Appendix A** for detailed description of parameter calculation).

3.1.2 Secondary Objective

- To validate the ability of the MBT to predict any hepatic decompensation event (considering all hepatic decompensation events as defined in section 8.4.1) using a second predefined cut-off of $\text{PDR}_{\text{peak}} \leq 7.5\%/\text{h}$.
- To validate the ability of the MBT to predict hepatic decompensation events within one year (for each of the two predefined cut-offs independently).
- To validate the ability of the MBT to predict hepatic decompensation events when using all the repetitions of the MBT measurements (time dependent parameter) (for each of the two predefined cut-offs independently).
- To validate the ability of the MBT to predict hepatic decompensation events within six months (for each of the two predefined cut-offs independently).
- To validate the ability of the MBT to predict new hepatic decompensation events (considering only reported hepatic decompensation events, as defined in section 8.4.2.5 as per Conatus protocol IDN-6556-17) as observed throughout the study (for each of the two predefined cut-offs independently).

3.1.3 Exploratory Objective

- To validate the ability of the MBT to predict specific types of hepatic decompensation events (for each of the two predefined cut-offs independently).
- To describe the change in MBT between the emricasan treatment arms and the placebo arm, thus assessing the response to treatment.

Exalenz Bioscience Ltd.	Last update: August 8, 2019
SAP for Protocol CON-EX-0217: Companion protocol for the ¹³C-Methacetin Breath Test using the BreathID® MCS System for Conatus phase 2 study of Emricasan, an Oral Caspase Inhibitor, under protocol IDN-6556-17 (IND111463)	Document Version: 1.0
Document N°: CSD00109	Page 7 of 21

3.1.4 Safety Objective

All adverse events, serious adverse events (SAE), suspected unexpected serious adverse reactions (SUSAR) and unanticipated adverse device effects (UADE) will be reported according to local regulations. No breath-test related adverse events are expected. For more information please refer to the Investigator's Brochure.

3.2 Study Endpoints

3.2.1 Primary Endpoint

The primary efficacy endpoint is the event-free survival (considering all hepatic decompensation events including events based on the reported AEs or SAEs, as defined in section 8.4.1).

3.2.2 Secondary Endpoints

The secondary efficacy endpoints for this study include:

- The event-free survival (considering all hepatic decompensation events including events based on the reported AEs or SAEs, as defined in section 8.4.1)
- The one-year event-free survival
- The event free survival when using all the repetitions of the MBT measurements (time dependent parameter).
- The six-month event-free survival
- The event-free survival (considering only reported hepatic decompensation events, as defined in section 8.4.2.5 as per Conatus protocol IDN-6556-17)

3.2.3 Exploratory Endpoints

- The specific type of hepatic decompensation event-free survival
- Absolute mean and percent mean change in MBT parameters between MBT visits (for each treatment arm)

Exalenz Bioscience Ltd.	Last update: August 8, 2019
SAP for Protocol CON-EX-0217: Companion protocol for the ¹³C-Methacetin Breath Test using the BreathID® MCS System for Conatus phase 2 study of Emricasan, an Oral Caspase Inhibitor, under protocol IDN-6556-17 (IND111463)	Document Version: 1.0
Document N°: CSD00109	Page 8 of 21

3.2.4 Safety Endpoint Measure

Safety endpoints includes all AE's in general and by seriousness, severity related to the MBT. No breath-test related adverse events are expected.

4 STUDY DESIGN

Please refer to Conatus' protocol IDN-6556-17.

This study is a companion protocol that will use the data generated by Conatus' study of emricasan under protocol IDN-6556-17. The IDN-6556-17 study is a Phase 2, multicenter, double-blind, randomized, placebo-controlled, dose-response study to evaluate the safety and efficacy of emricasan in improving event-free survival based on a composite clinical endpoint (where all-cause mortality, new decompensation events, and Model for Endstage Liver Disease (MELD) score progression are counted as events as defined in section 8.4.2.5) in subjects with decompensated NASH cirrhosis.

The study treatment duration will be at least 48 weeks with study visits every 4 weeks up to week 48 and every 8 weeks after week 48. All subjects will continue treatment until the last subject in the study reaches 48 weeks in the study. This subject will undergo the assessments of the final treatment visit at week 48. For all other subjects, the final treatment visit should take place on their last study visit prior to or on the day of the final treatment visit of the last subject who has been in the study for 48 weeks.

As part of the IDN-6556-17 study, the MBT will be performed during a screening visit, every 24 weeks and at the final treatment visit, to assess whether emricasan compared to placebo improves liver metabolic function as determined by the Methacetin Breath Test.

The data obtained in this study will be sequestered from Exalenz in order to allow potential pooling of the data received from Conatus' study as well as other parallel recruiting studies, if applicable, where both the MBT and clinical outcome (e.g. hepatic decompensation events) will be available. Once sufficient data will be accrued, it will be used to validate the algorithm

Exalenz Bioscience Ltd.	Last update: August 8, 2019
SAP for Protocol CON-EX-0217: Companion protocol for the ¹³C-Methacetin Breath Test using the BreathID® MCS System for Conatus phase 2 study of Emricasan, an Oral Caspase Inhibitor, under protocol IDN-6556-17 (IND111463)	Document Version: 1.0
Document N°: CSD00109	Page 9 of 21

developed using data from IDE# G080227 and other clinical data accumulated by Exalenz to date. Additional analyses may be performed by Exalenz on the data to be received from this Conatus study after validation of the aforementioned algorithm.

4.1 Sample Size Considerations

The plan is to enroll a subset of subjects that will be screened under Conatus' IDN-6556-17 study. This Conatus study plans to enroll 210 subjects (70 subjects per treatment arm) to be randomly assigned to 1 of 3 treatment groups, 2 doses of emricasan (25 mg or 5 mg) or placebo in a 1:1:1 ratio. A 45% screen failure (SF) rate is estimated. It is expected that approximately 90% of the patients enrolled will perform the MBT. The total number of MBT results expected ranges between 120 and 310 at screening and up to 200 at respective study visits with 24-week intervals and at the final treatment visit.

5 GENERAL CONSIDERATIONS FOR HANDLING OF MISSING DATA

5.1 Premature Withdrawal and Missing Data

For patients who are withdrawn from the study prior to study completion, all data compiled up to the point of discontinuation will be used for analysis. All withdrawals will be included in all analyses up to the time of withdrawal.

There will be no imputation for missing data.

6 SIGNIFICANCE LEVELS AND HANDLING OF TYPE I ERROR

6.1 Type I Error

The overall significance level for this study is 5% using two-tailed tests, except for treatment by site interaction that will be tested at a significance level of 10%.

Exalenz Bioscience Ltd.	Last update: August 8, 2019
SAP for Protocol CON-EX-0217: Companion protocol for the ¹³C-Methacetin Breath Test using the BreathID® MCS System for Conatus phase 2 study of Emricasan, an Oral Caspase Inhibitor, under protocol IDN-6556-17 (IND111463)	Document Version: 1.0
Document N°: CSD00109	Page 10 of 21

6.2 *Hierarchy Approach for Secondary Endpoint Analysis*

The hierarchy approach will be adopted for the primary and secondary endpoints to control type I error due to multiple endpoint testing. Thus the primary endpoint will first be analyzed and only if $p < 0.05$, will the secondary endpoint be analyzed. This approach will maintain the overall study type I error by continuing to analyze the next end-point in the hierarchy only if the previous endpoint analysis was found significant. The hierarchy approach is extended for the secondary endpoints as well, according to the order that they appear in section 3.2.2 above.

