8.4.2 Secondary Endpoints

8.4.2.1 The overall event-free survival with a second predefined cut-off

The event free survival will be analyzed in the same manner as the primary endpoint analysis with the exception that the dichotomous MBT result will be based on a second predefined cut-off: Any PDR_{peak} value of less or equal to 7.5 %/h (see **Appendix A** for detailed description of parameter calculation) will be considered as 'high risk' and any value above that threshold will be considered as 'lesser risk'.

Exalenz Bioscience Ltd.	Last update: August 8, 2019
SAP for Protocol CON-EX-0217: Companion protocol for the ¹³C-Methacetin Breath Test using the BreathID® MCS System for Conatus phase 2 study of Emricasan, an Oral Caspase Inhibitor, under protocol IDN-6556-17 (IND111463)	Document Version: 1.0
Document N°: CSD00109	Page 15 of 21

8.4.2.2 *The one-year event-free survival*

The one-year event free survival will be analyzed in the same manner as the primary endpoint analysis with the exception of censoring all subjects after 1 year (365 days) from baseline MBT date.

This analysis will be repeated while using the second pre-defined cut-off described in the first secondary endpoint (section 8.4.2.1).

8.4.2.3 *The event free survival when using all the repetitions of the MBT measurements (time dependent parameter)*

The event free survival will be analyzed in the same manner as the primary endpoint analysis with the exception of using all repetitions of the MBT measurements while dividing the prediction times to the intervals between tests by applying the Time dependent covariate method.

This analysis will be repeated while using the second pre-defined cut-off described in the first secondary endpoint (section 8.4.2.1).

8.4.2.4 *The six-month event-free survival*

The six-month event free survival will be analyzed in the same manner as the primary endpoint analysis with the exception of censoring all subjects after six months (180 days) from baseline MBT date.

This analysis will be repeated while using the second pre-defined cut-off described in the first secondary endpoint (section 8.4.2.1).

8.4.2.5 *The event-free survival considering only new hepatic decompensation events as defined in Conatus study protocol IDN-6556-17*

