The event free survival will be analyzed in the same manner as the primary and secondary endpoint analyses (sections 8.4.1, 8.4.2.1, 8.4.2.3 and 8.4.2.4) taking only hepatic decompensation events into consideration as defined and adjudicated in the Conatus study protocol IDN-6556-17:

1. All-cause mortality
2. New decompensation events

Exalenz Bioscience Ltd.	Last update: August 8, 2019
SAP for Protocol CON-EX-0217: Companion protocol for the ¹³C-Methacetin Breath Test using the BreathID® MCS System for Conatus phase 2 study of Emricasan, an Oral Caspase Inhibitor, under protocol IDN-6556-17 (IND111463)	Document Version: 1.0
Document N°: CSD00109	Page 16 of 21

- a. Variceal hemorrhage (including recurrent variceal hemorrhage) documented by endoscopy and requiring hospitalization
- b. New onset ascites requiring diuretics (in a subject without prior history of ascites requiring diuretics)
- c. New onset HE \geq grade II requiring hospitalization in the absence of other comorbidities or alternative causes (in a subject without prior history of HE \geq grade II)
- d. Hepatorenal syndrome requiring hospitalization (either type 1 or 2)
- e. SBP requiring hospitalization

3. MELD score progression defined as any increase \geq 4 points from baseline

This analysis will be repeated while using the second pre-defined cut-off described in the first secondary endpoint (section 8.4.2.1).

8.4.3 *Exploratory Endpoints*

8.4.3.1 *The specific hepatic decompensation type event free survival*

The specific types of hepatic decompensation events or combinations of them for event free survival will be analyzed in a similar manner as the primary endpoint analysis. The following list contains all the separate analyses that will be performed:

1. All-cause mortality
2. Liver-specific mortality
3. Liver-specific mortality **or** liver transplant
4. Liver transplant
5. Variceal hemorrhage that required ‘non-drug therapy’ (e.g. variceal ligation, sclerotherapy) based on the AE log or requiring hospitalization **or** portal hypertensive gastropathy hemorrhage requiring hospitalization
6. Variceal hemorrhage that required ‘non-drug therapy’ (e.g. variceal ligation, sclerotherapy) based on the AE log or requiring hospitalization **or** portal hypertensive gastropathy hemorrhage requiring hospitalization **or** occurrence of

Exalenz Bioscience Ltd.	Last update: August 8, 2019

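### The SAP's testing hierarchy does not hold the 5% error it claims: from the second secondary endpoint on, each step contains two or more 5% tests and no rule for passing it

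*SAP*

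**What the plan says.** SAP 6.1 sets an overall two-sided level of 5%. Section 6.2 applies a hierarchy to the primary and secondary endpoints and states its effect: "This approach will maintain the overall study type I error by continuing to analyze the next end-point in the hierarchy". The condition for moving from one step to the following one is put in the singular: "only if the previous endpoint analysis was found significant". The secondary endpoints are taken "according to the order that they appear in section 3.2.2 above".

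Section 3.2.2 lists five secondary endpoints and names no cut-off for any of them. The last is "The event-free survival (considering only reported hepatic decompensation events, as defined in section 8.4.2.5 as per Conatus protocol IDN-6556-17".

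The analyses themselves are in 8.4:

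- **Primary (8.4.1):** overall event-free survival, 5.5 %/h.
- **Secondary 1 (8.4.2.1):** overall event-free survival, 7.5 %/h.
- **Secondary 2 to 4 (8.4.2.2 to 8.4.2.4; one-year, time-dependent, six-month):** analysed as the primary is, and then "This analysis will be repeated while using the second pre-defined cut-off described in the first secondary endpoint (section 8.4.2.1".
- **Secondary 5 (8.4.2.5; events as defined in the main study):** analysed "in the same manner as the primary and secondary endpoint analyses (sections 8.4.1, 8.4.2.1, 8.4.2.3 and 8.4.2.4", again with a repeat at the second cut-off.

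Section 3.1.2 makes both cut-offs secondary objectives for endpoints 2 to 5. For the fifth it reads "as observed throughout the study (for each of the two predefined cut-offs independently". Section 8.1 says that p-values are nominal and intervals unadjusted.

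**The concern.** A fixed sequence protects the family-wise error because each position holds one full-level test, and a later position is reached only after every earlier one has been rejected. Once a position holds two full-level tests and either can support a claim, protection at that position is lost whenever the earlier effects are real. That is the situation in which the later positions are reached.

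Section 6.2 speaks of one analysis per endpoint, while 8.4.2 supplies two or more. If the one-year result is significant at 5.5 %/h and not at 7.5 %/h, the SAP does not say whether a claim may be made or whether testing goes on. That decision would then be taken with the results in view, in a study meant to validate cut-offs fixed in advance.

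**Working it through.** **Number of tests per step in the principal (per-protocol) set**

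| Step | Tests |
|---|---|
| Primary, overall | 1 (5.5) |
| Secondary 1, overall | 1 (7.5) |
| Secondary 2, one-year | 2 |
| Secondary 3, time-dependent | 2 |
| Secondary 4, six-month | 2 |
| Secondary 5, main-study events | 2 if only the overall analysis counts; 6 if overall, time-dependent and six-month all count at both cut-offs |

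**The plan's own figure.** One test per step in fixed order gives 5%. Simulating six single-test steps under the global null gave 5.02%. The primary and secondary 1 therefore meet the stated level. From secondary 2 on, 5% is recovered only by adding a rule that the SAP does not contain.

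**Two-test step.** Take the earlier steps as passed on real effects and both nulls in the step as true. The cut-offs are nested on the same subjects. With p1 the share at or below 5.5 and p2 the share at or below 7.5, the correlation of the two dichotomies is r = sqrt[p1(1 − p2) / (p2(1 − p1))]. The documents give neither share, so these are assumptions. For example, 25% and 50% give r = sqrt(0.25 × 0.50 / (0.50 × 0.75)) = 0.58. The error is P(|Z1| > 1.96 or |Z2| > 1.96) for a bivariate normal; the last column equals 10% minus that.

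| p1 / p2 | r | Either significant | Both significant |
|---|---|---|---|
| 25% / 65% | 0.42 | 9.3% | 0.7% |
| 25% / 50% | 0.58 | 8.8% | 1.2% |
| 50% / 65% | 0.73 | 8.2% | 1.8% |
| 40% / 55% | 0.74 | 8.2% | 1.8% |
| 50% / 55% | 0.90 | 7.0% | 3.0% |

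For independent tests the error is 1 − 0.95² = 9.75%. The upper bound is 2 × 5% = 10%.

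**Possible pass rules**

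- *Both cut-offs needed to move on, but each claimable by itself:* still 8.2-9.3% at r = 0.42 to 0.73. The gate acts after the false claim has been made.
- *Both needed before any claim at that step:* the last column if both nulls are true, and at most 5% if one is.
- *Fixed order, 5.5 and then 7.5:* 5.0% at each r.
- *Alpha split, 2.5% each:* at most 5%.

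**Secondary 5 with six tests.** The correlation is modelled as the cut-off correlation (2 × 2) crossed with a common between-analysis correlation (3 × 3), with all six nulls true.

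| Between-analysis correlation | Cut-off r = 0.42 | Cut-off r = 0.73 |
|---|---|---|
| 0.6 | 21.2% | 18.7% |
| 0.7 | 19.6% | 17.4% |
| 0.8 | 17.8% | 15.7% |
| 0.9 | 15.2% | 13.4% |

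With cut-offs as close as 50% / 55% (r = 0.90), the lowest value is about 11.4%. If only the two overall tests count, the two-test table applies.

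The range 0.6 to 0.9 is an assumption. Under the null, a censored and a full log-rank statistic correlate at about sqrt(events by the cut / all events). Assume a constant hazard, a one-year risk of 20-50%, and follow-up spread evenly from 336 days to a maximum of 336-900 days. Six-month against overall is then 0.58-0.78. The time-dependent analysis is taken to lie in the same range.

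**The case against.** The strongest reply is that the SAP can be read as already having one formal test per step. Sections 8.4.2.2 to 8.4.2.4 first define each analysis as the primary one, hence at 5.5 %/h, and only then repeat it. Appendix A presents 7.5 %/h as a second cut-off, and 6.2 speaks of the previous analysis in the singular. The same repeat sentence also closes the exploratory section, where no formal claim is made. On this reading 5% holds for secondary 2 to 4. It is a fair reading, but it is not written down. Section 3.1.2 sets an objective for each cut-off separately, and 7.5 %/h is itself the formal test in secondary 1. Protocol 9.3, which aims to validate at least one cut-off and leaves success criteria to later regulatory discussion, gives no pass rule for a step; if anything it favours the either-or reading that inflates the error.

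A second reply is that later nulls are rarely true once earlier effects are real. This largely stands for the one-year step, which repeats the primary analysis "with the exception of censoring all subjects after 1 year (365 days) from baseline MBT date", and for the six-month step: a null there needs an effect that appears only late. It has less force for the time-dependent step, which uses a different exposure, and for secondary 5, which uses a different event definition including all-cause mortality. Even there the overlap with the primary is considerable, because the baseline breath test serves until the first repeat and most event types are shared. The percentages are therefore error rates under stated nulls, and they do not forecast how often a false claim will occur.

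Third, the six-test count is the least certain. Section 3.2.2 lists one endpoint, and the wording in 3.1.2 points to the overall analysis, so two tests is a reasonable count. The SAP does not settle it.

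Finally, the nominal p-values in 8.1 describe reporting. They neither withdraw the control claimed in 6.2 nor supply a pass rule.

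**Conclusion.** The concern holds. Section 6.2 claims a 5% control that the procedure as written gives only for the primary and the first secondary endpoint. With either cut-off claimable, a two-test step carries about 8-9% when its nulls are true and the earlier effects real. This assumes 25-50% of subjects at or below 5.5 %/h and 50-65% at or below 7.5 %/h, at least 15 points apart. It falls to 7.0% for closer cut-offs and cannot exceed 10%. The main-study-event step carries the same 8-9% with two tests, or about 13-21% with six at cut-off correlations of 0.42 to 0.73.

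The primary conclusion is untouched, and if no effect exists anywhere the error stays at or below 5%. The weakness is confined to later secondary claims. It should be corrected, but it does not threaten the study's main result.

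**What to change.** In 6.2, write one sequence with a single 5% test per position in the per-protocol set, naming the cut-off each time. For example: overall 5.5, overall 7.5, one-year 5.5, one-year 7.5, time-dependent 5.5, time-dependent 7.5, six-month 5.5, six-month 7.5, main-study events overall 5.5, main-study events overall 7.5. Alternatively, name 5.5 %/h as the only formal test in each step after secondary 1 and label the 7.5 %/h repeats supportive.

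Under either choice, label the time-dependent and six-month re-runs in 8.4.2.5 and the intent-to-diagnose repeats as supportive. If a rule requiring both cut-offs is preferred, it must apply to any claim at that step and not only to moving on.

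The cost is SAP wording, and SAP section 2 allows amendment until the sponsor accesses the data. In the single chain, a failure at one cut-off ends all later formal claims. In the alternative, 7.5 %/h results after secondary 1 carry no formal claim.
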